OSU Study #: OSU-17160
IRB Protocol #: 2017C0132
Version: Amendment 3: 12/19/2017
IRB Approved: 04/24/2018

**Phase II Study of Lenalidomide in Combination with Nivolumab
In Patients with Relapsed/Refractory Multiple Myeloma**

Clinical Lead (PI): **[name], MPH**
E-mail: [contact]

Scientific Lead: **[name]**
Email: [contact]

Clinical Site PI: **[name]**
Beth Israel Deaconess
Medical Center
Email: [contact]

Study Sponsor: **The Ohio State University**
IND #: 135711

Funding Entity: **American Cancer Society**
Drug Supplied: **Nivolumab**
Drug Supplier: **Bristol-p Squibb**

Multi-Center Trial Program: **Clinical Trials Office**
The Ohio State University Comprehensive Cancer Center
[contact]
E: [contact]

Initial: 28 Apr 2017
Amendment 1: 28 Sep 2017
Amendment 2: 29 Nov 2017
Amendment 3: 19 Dec 2017

PROTOCOL SYNOPSIS

Study Title	Phase II Study of Lenalidomide in Combination with Nivolumab in Patients with Relapsed/Refractory Multiple Myeloma
Study ID	
Sponsor	American Cancer Society
Primary Objectives	To determine the efficacy of Nivolumab in combination with lenalidomide (Revlimid) in terms of overall response rate in patients with relapse/refractory multiple myeloma (MM)
Primary Endpoint	
 • To determine the overall response rate (ORR) after 4 cycles and then at 8 and 12 months in responding patients according to the International Myeloma Working Group (IMWG) response criteria in the phase II study.
Secondary Endpoints	
 • To determine time to progression (TTP) and progression free survival (PFS) • To determine overall survival (OS) • To assess Nivolumab correlative biologic studies to assess immunomonitoring of lymphocytes subsets including T and NK cell, and ex-vivo assessment of immune functional activities.
Safety parameters	Infusion related and treatment emergent toxicities per National Cancer Institute Common Terminology Criteria for Adverse Events (NCI CTCAE) v4.0
Study Design	
Nivolumab will be administered intravenously as a 1-hour infusion, 240 mg every 2 weeks (day 1 and 15) of each 28 day cycle. At the treating physician's discretion, patients will receive pre-medication (Tylenol 650mg or Ibuprofen 800mg or related medication), and an antihistamine (phenergan 25mg or equivalent) before Nivolumab infusion. Lenalidomide will be given at starting dose of 25 mg days 1-21 of a 28 day cycle.
 
Patients will be assessed for response at the end of each cycle according to the IMWG response criteria.
 
Patients will be monitored for safety by assessing toxicities as graded by the NCI CTCAE v4.0. Dose limiting toxicity (DLT) will be defined as one or more of the following toxicities considered to be at least possibly related to one of the study drugs during Cycle 1
 
 • Grade 3 or greater nonhematologic toxicity with the exception of Grade 3 nausea, vomiting and diarrhea that responds to supportive therapy. • Grade 4 thrombocytopenia, or grade 3 thrombocytopenia with bleeding, or any requirement for platelets transfusion • Grade 4 neutropenia persisting for more than 5 days. • Grade 3 or greater febrile neutropenia (temperature $\geq 38.5^{\circ}\text{C}$) • Grade 4 anemia, unexplained by underlying disease 
Patients that experience a lenalidomide-related hematologic DLT may continue on therapy if the event resolves, the investigator considers it in the best interest of the patient to continue and the patient qualifies for initiation of the next cycle with standard of care lenalidomide dose reduction.

	
Discontinuation of treatment due to disease progression will not constitute a DLT.
 
After 4 cycles of therapy or earlier if clinically indicated, response determination will be assessed by the IMWG criteria. At the end of Cycle 4, if a subject has responded (complete or partial response) or has stable disease, dosing with Nivolumab and lenalidomide will continue for a minimum of 8 additional cycles or until disease progression or withdrawal.
 
If disease progression is observed at the end of Cycle 4 evaluation, all study therapy will be discontinued. Confirmation of progression of disease will be done according to the IMWG criteria.
 
Following the 30-day post-treatment follow-up assessment, additional evaluations will occur once per month (unless subject discontinued due to progression) until the earliest of the following events: disease progression, the time of initiation of new therapy, death or study completion.
 
Study completion is defined as 30 days after the last subject remaining on study medication discontinues study medication.
 
An independent Data Monitoring Committee will continue oversight of this trial.
 
Treatment will continue until Progression of disease, death, unacceptable toxicity or patient or treating physician decision to discontinue therapy.

Dosing Regimen	Nivolumab will be given at a dose of 240 mg every 2 wks (Day 1 and 15) of a 28-day cycle. Lenalidomide will be given at starting dose of 25 mg days 1-21 of a 28 day cycle. Dexamethasone can be added after 2 cycles if stable disease.
Planned Sample size	18 patients will be recruited
Duration of Study Period	
Patient will continue study treatment at the treating physician's discretion. Patients achieving at least a stable disease can continue treatment until progression of disease, death, unacceptable toxicity, or patient decision. Overall response will be assessed after 4, 8, and 12 cycles.
 
The total study enrollment period is expected to be up to 12-18 months.

Eligibility	
Inclusion criteria
 
 Patients must be at least 18 years of age with evidence of progression, relapse or refractory disease from last line of therapy as defined by IMWG criteria and measurable disease as defined by any of the following: 
 Serum M-protein ≥ 0.5 g/dl (≥ 10 g/l) Urine monoclonal protein ≥ 200 mg/24h Involved FLC level ≥ 10 mg/dl (≥ 100 mg/l) and an abnormal serum free light chain ratio (<0.26, or >1.65)

	
Measurable biopsy proven plasmacytoma (should be measured within 28 days of initial investigational agent dosing)
 
 Patients must have exhausted all available therapies known to provide clinical benefit and has progressed, relapsed or is refractory to last line of treatment. Patients must have had at least 4 prior lines of therapy. Patient may be enrolled at any time from last line of therapy Patients must have ANC > 1000/μL; Platelets \geq75,000/μL, if plasma cell percentage on bone marrow biopsy aspirate or core is > 30%, platelet eligibility requirement will be adjusted to 60,000/μl. Patients must have adequate hepatic function as evidenced by: total bilirubin \leq 1.5 mg/dL, alkaline phosphatase \leq 3X the ULN, AST/ALT \leq 2X the ULN Patients must have adequate renal function as evidenced by serum creatinine \leq 2mg/dL or calculated creatinine clearance of \geq 40ml/min within 14 days of registration using MDRD formula. Patient must be able to swallow capsule or tablet. Patients must provide informed consent. Patients must have a left ventricular ejection fraction \geq 30%, no uncontrolled arrhythmias or New York Heart Association class III-IV heart failure. Patients must have a Karnofsky performance status \geq 70. A negative pregnancy test will be required for all women of child bearing potential. Breast feeding is not permitted. Fertility requirements 
 Female patients with child bearing potential must have a negative pregnancy test at least 7 days before starting treatment drugs. Male patients must agree to use an adequate method of contraception for the duration of the study and for 7 months afterwards. Female patients must be either post-menopausal, free from menses \geq2 yrs, surgically sterilized, willing to use two adequate barrier methods of contraception to prevent pregnancy, or agree to abstain from sexual activity starting from screening and for 5 months afterwards. Female patients of child bearing potential must agree to comply with the fertility and pregnancy test requirements dictated by the Rev-Assist program.
--	--

Exclusion Criteria

- Patients with peripheral neuropathy > CTCAE grade 2
- Patients receiving concurrent corticosteroids at the time protocol therapy is initiated other than for physiologic maintenance treatment.
- History of allergic reaction (including erythema nodosum) to lenalidomide
- Concurrent use of complementary or alternative medicines that would confound the interpretation of toxicities and antitumor activity of the study drugs.
- Patients with contraindication to thromboprophylaxis
- Unacceptable cardiac risk factors defined by any of the following criteria: Patients with congenital long QT syndrome, any history of ventricular fibrillation

	
or torsade de pointes, bradycardia defined as HR< 50 bpm, Left ventricular ejection fraction < 30%
 
 • Patients who have received targeted or investigational agents within 2 weeks or within 5 half-lives of the agent and active metabolites (whichever is longer) and who have not recovered from side effects of those therapies. • Patients who have undergone major surgery ≤ 2 weeks prior to starting study drug or who have not recovered from the side-effects of surgery • Patients with known positivity for human immunodeficiency virus (HIV), or hepatitis C. Baseline testing for HIV and hepatitis C is not required • Patients with a history of another primary malignancy that is currently clinically significant or currently requires active intervention, other than non-melanoma skin cancer and carcinoma in situ of the cervix should not be enrolled. Patients are not considered to have a “currently active” malignancy if they have completed therapy for a prior malignancy, are disease free from a prior malignancy for ≥ 5 yrs and are considered by their physician to be less than 30% risk of relapse. • Patients with active (untreated or relapsed) CNS metastasis of the patient’s myeloma. • Patients with a history of gastrointestinal surgery or other procedure that might, in the opinion of the investigator(s), interfere with the absorption or swallowing of the study drugs. • Patients with any significant history of non-compliance to medical regimens or unwilling or unable to comply with the instructions given to them by the study staff. • Any other medical condition, including mental illness or substance abuse, deemed by the investigator(s) to likely interfere with the patient’s ability to sign informed consent, cooperate and participate in the study, or interfere with the interpretation of the results.
--	---

Contents

1	BACKGROUND AND RATIONALE	9
1.1	Multiple Myeloma	9
1.2	NK cells and MM.....	9
1.3	Lenalidomide (Revlimid).....	9
1.3.1	Clinical Experience in Relapsed Multiple Myeloma	9
1.4	Nivolumab.....	11

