3 ELIGIBILITY CRITERIA

3.1 Inclusion Criteria

- Patients must be at least 18 years of age with evidence of progression, relapse or refractory disease from last line of therapy as defined by IMWG criteria. A line of therapy is defined as one or more cycles of a planned treatment program which may be one therapy or a sequence of treatments. A new line of therapy begins when a planned course of therapy is modified due to disease progression, relapse or toxicity or when a planned period of observation off therapy.
Measurable disease as defined by any of the following:
 - Serum M-protein ≥ 0.5 g/dl (≥ 10 g/l)
 - Urine monoclonal protein ≥ 200 mg/24h
 - Involved FLC level ≥ 10 mg/dl (≥ 100 mg/l) and an abnormal serum free light chain ratio (<0.26 , or >1.65)
 - Measurable biopsy proven plasmacytoma (should be measured within 28 days of initial investigational agent dosing)
- Patients must have exhausted all available therapies known to provide clinical benefit and has progressed, relapsed or is refractory to last line of treatment.
- Patients must have had at least 4 prior lines of therapy.
- Patient may be enrolled at any time from last line of therapy.
- Patients must have ANC $> 1000/\mu\text{L}$; Platelets $\geq 75,000/\mu\text{L}$, if plasma cell percentage on bone marrow biopsy aspirate or core is $> 30\%$, platelet eligibility requirement will be adjusted to $60,000/\mu\text{L}$.
- Patients must have adequate hepatic function as evidenced by: total bilirubin ≤ 1.5 mg/dL, alkaline phosphatase $\leq 3X$ the ULN, AST/ALT $\leq 2X$ the ULN
- Patients must have adequate renal function as evidenced by serum creatinine ≤ 2 mg/dL or calculated creatinine clearance of ≥ 40 ml/min within 14 days of registration using MDRD formula.
- Patient must be able to swallow capsule or tablet.
- Patients must provide informed consent.
- Patients must have a left ventricular ejection fraction $\geq 30\%$, no uncontrolled arrhythmias or New York Heart Association class III-IV heart failure.
- Patients must have a Karnofsky performance status ≥ 70 .
- A negative pregnancy test will be required for all women of child bearing potential. Breast feeding is not permitted.
- Fertility requirements
 - Female patients with child bearing potential must have a negative pregnancy test at least 7 days before starting treatment drugs.
 - Male patients must agree to use an adequate method of contraception for the duration of the study and for 7 months afterwards.

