4 SUBJECT REGISTRATION PROCEDURES

For subsite patients, sites must send the signed consent form, documentation of the consent process, and the Screening Form (refer to Supplemental Forms Document) within 2 business days of initial consent.

Patients will be registered after meeting all entry requirements and signing of the informed consent document.

OSU patients will be registered by the OSU research coordinator, as per CTO standard practice. Subsite patients will have eligibility verified and will be entered on study centrally at The Ohio State University by the Multi-Center Trial Program (MCTP). All subsites must email the MCTP to verify slot availabilities prior to consenting patients. Once a patient signs consent, the signed consent document and documentation of the consenting process must be faxed or securely emailed to the MCTP. The required forms, including Eligibility Criteria Checklist and Registration Form, can be found in the Supplemental Forms Document.

To register a subsite patient, the following documents must be completed by the subsite research team and faxed or securely e-mailed to the MCTP:

- Copy of all baseline tests required per the protocol calendar. Tests must be within the specified window.
- Signed Patient Consent Form, if not previously sent
- Signed Patient HIPAA Authorization Form (if separate), if not previously sent
- Consent Documentation Note, if not previously sent
- Completed & Signed Eligibility Checklist (refer to Supplemental Forms Document)
- Registration Form (refer to Supplemental Forms Document)
- Source documents verifying every inclusion & exclusion criteria

Upon receipt of registration documents, the MCTP will send an email confirming receipt. If confirmation of receipt is not received within 1 hour of submission, please contact the MCTP by phone and/or pager to confirm receipt.

Upon receipt of all required registration documents and upon verification the subsite patient meets all eligibility criteria, the MCTP will:

- Assign the patient a study sequence ID, if not already provided at time of consent
- Register the patient on the study
- Fax and/or e-mail the subsite the completed Registration Form with the assigned study sequence ID and registration date as confirmation of patient registration

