The proportion of responses (partial and complete) will be calculated out of all eligible patients who receive any treatment in that disease group who are included in the phase II assessment. Assuming the number of responses is binomially distributed, 95% binomial confidence intervals will also be calculated for the estimate of the proportion of responses. All adverse events will be summarized by the NCI CTCAE v. 4 criteria, and tabulated across all patients who received any treatment with a focus on severe (grade 3+) adverse events and toxicities (i.e. those deemed at least possibly related to study treatment). In addition, we will summarize the proportion of patients who received dexamethasone after being stable disease but without response after 2 cycles of therapy. We will descriptively summarize how many of these patients were converted to response after the addition of dexamethasone. Since the addition of dexamethasone is part of the overall treatment regimen that is dependent on treatment outcome at a certain time point, we will not make other adjustments to the study design to evaluate these patients separately outside of this descriptive summarization of whether or not they received the dexamethasone. We will evaluate other clinical outcomes such as progression-free survival and overall survival using the methods of Kaplan-Meier, although these analyses will be exploratory and primarily to help describe the cohort itself.

Correlative analyses will also be done, including analysis of markers of the immunogenicity of nivolumab. In particular, we will evaluate biological and cellular markers in patients treated with nivolumab, measure PD-L1 expression on MM cells, percentage increase in NK cell activity, migration, immune complex formation, and cytotoxicity. Other markers such as plasma cell IHC baseline expression to characterize immunologic markers of MM cells that are responsive to nivolumab such as TNF-alpha, IFN-gamma, CD4, CD8, and granzyme B will be evaluated in addition to markers of MM cells responsive to lenalidomide (Sparc, IRF-4). Changes in these markers before and after therapy will be explored using graphical analyses as well as summarized quantitatively. We will also explore how changes in these correlative markers may differ based on whether or not the patient achieved a response or not; to accomplish this, we will utilize different plotting characters and colors for successes

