		70	Cares for self, unable to carry on normal activity or to do active work.
2	In bed <50% of the time. Ambulatory and capable of all self-care, but unable to carry out any work activities. Up and about more than 50% of waking hours.	60	Requires occasional assistance, but is able to care for most of his/her needs.
		50	Requires considerable assistance and frequent medical care.
3	In bed >50% of the time. Capable of only limited self-care, confined to bed or chair more than 50% of waking hours.	40	Disabled, requires special care and assistance.
		30	Severely disabled, hospitalization indicated. Death not imminent.
4	100% bedridden. Completely disabled. Cannot carry on any self-care. Totally confined to bed or chair.	20	Very sick, hospitalization indicated. Death not imminent.
		10	Moribund, fatal processes progressing rapidly.
5	Dead.	0	Dead.

13 Appendix. IMWG Response Criteria

Serum and urine M-protein estimates will be performed every 4 weeks; except for assessment of CR, patients with measurable disease restricted to the SPEP (or UPEP) will need to be followed only by SPEP (or UPEP). Responses will be assessed according to the criteria of the International Myeloma Working Group⁴⁶, and characterized as follows:

Response Category	Response Criteria ^a
SCR	CR as defined below plus 
 • Normal FLC ration and • Absence of clonal cells in bone marrow^b by immunohistochemistry or immunofluorescence^c
CR	Negative immunofixation on the serum and urine and disappearance of any soft tissue plasmacytomas and $\leq 5\%$ plasma cells in bone marrow ^b
VGPR	Serum and urine M-protein detectable by immunofixation but not on electrophoresis or 90% or greater reduction in serum M-protein plus urine M-protein level < 100 mg per 24 hours

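### The serum M-protein entry criterion prints two thresholds that differ two-fold: 0.5 g/dl is 5 g/l, not 10 g/l

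*Combined protocol and SAP*

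**What the plan says.** The eligibility part of the synopsis and section 3.1 (Inclusion Criteria) list the same four ways to qualify. The serum line in both reads "Serum M-protein ≥ 0.5 g/dl (≥ 10 g/l". The free light chain (FLC) line reads "Involved FLC level ≥ 10 mg/dl (≥ 100 mg/l" and adds an abnormal ratio. The other two routes are urine monoclonal protein of at least 200 mg/24h and a measurable, biopsy-proven plasmacytoma. Section 3.1 introduces the list with "Measurable disease as defined by any of the following", so the routes are alternatives.

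The response appendix (section 13, IMWG Response Criteria) has its own definition of measurable disease in footnote d: at least one of serum M-protein ≥1 g/dl, urine M-protein ≥200 mg/24h, or involved FLC ≥10 mg/dl with an abnormal ratio. The marker for footnote d is attached to the word for unmeasurable M-protein in the partial response (PR) row.

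For the analysis, section 7.1.1 states: "The proportion of responses (partial and complete) will be calculated out of all eligible patients who receive any treatment". Section 7.3 divides the response rate by per protocol patients instead.

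**The concern.** A threshold given in two units must be one threshold. Here the two figures define different entry rules, and nothing in the documents says which one governs.

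The patients concerned have serum M-protein in the band between the two figures, urine below 200 mg/24h, no qualifying FLC and no measurable plasmacytoma. For them, eligibility depends on which half of the line the person checking has read. That matters beyond record keeping, because section 7.1.1 builds its response proportion on eligible treated patients. The decision cut-offs there (7 or fewer, 8 or 9, 10 or more) are written for 18 patients. If one treated patient were later ruled ineligible, the denominator would be 18 − 1 = 17, for which no cut-offs are given. This is conditional: the documents do not show that any such patient will be enrolled.

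A second, weaker issue arises only if the g/dl figure governs. A serum value accepted as measurable at entry would then lie below the threshold in footnote d, which leaves some doubt about the marker used to score response and progression.

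**Working it through.** **Inputs**

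- Serum M-protein entry line, synopsis and section 3.1: 0.5 g/dl, with 10 g/l in brackets.
- FLC entry line, same lists: 10 mg/dl, with 100 mg/l in brackets.
- Section 13, footnote d: serum M-protein 1 g/dl.

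**Formula.** One litre is 10 dl, so a value in g/dl × 10 gives g/l, and a value in g/l ÷ 10 gives g/dl.

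**Step 1: check the factor on a line that should reproduce.** FLC: 10 mg/dl × 10 = 100 mg/l. The plan prints 100 mg/l, so this line is correct.

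**Step 2: apply it to the serum line.** 0.5 g/dl × 10 = 5 g/l. The plan prints 10 g/l, so this line does not reproduce.

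**Step 3: reverse.** 10 g/l ÷ 10 = 1.0 g/dl. The plan prints 0.5 g/dl.

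**Step 4: size.** 10 g/l ÷ 5 g/l = 2.0.

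**Step 5: compare with footnote d.** 1 g/dl × 10 = 10 g/l. Footnote d equals the bracketed entry figure and is twice the g/dl entry figure.

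**Step 6: who is affected at entry.** The band is 0.5 to <1.0 g/dl, that is 5 to <10 g/l. Patients in it meet the g/dl figure and fail the g/l figure. A patient in the band who qualifies by urine, FLC or plasmacytoma is eligible either way.

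**Step 7: scoring, if the g/dl figure governs.** Three features of section 13 favour ordinary serum scoring for patients in the band:

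- The first PR line, on reduction of serum and urine M-protein, carries no threshold.
- Footnote d can be read as limiting only the substitute markers.
- The lead-in says "patients with measurable disease restricted to the SPEP (or UPEP) will need to be followed only by SPEP (or UPEP".

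Against this, the PR row moves to FLC when M-protein is unmeasurable, and that word points to footnote d. A reader can therefore class a value in the band as unmeasurable and use the substitute. In the progressive disease row, the FLC arm is reserved for patients without measurable serum and urine M-protein, so the same question arises there. Complete response and both arms of very good partial response (the second begins "90% or greater reduction in serum M-protein plus urine M-protein level") carry no link to footnote d and are unaffected.

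**The case against.** The strongest reply is that this is a slip with no demonstrated consequence. The n=18 design and its cut-offs do not depend on the serum threshold. The affected group is narrow and may be empty. Both registration routes end at the sponsor's institution, and subsite eligibility is recorded on a checklist in a separate forms document that is not part of this review and may print a single figure. All of that stands, and it limits the claim to what is printed: the protocol's own criterion has two values. It does not make that criterion usable for a patient in the band. An extraction fault is unlikely, because the same text stands in two separately formatted places and the adjacent FLC line is correct.

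A reader might infer more than the documents support in four ways.

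- *That 10 g/l was intended, because footnote d agrees with it.* The agreement is suggestive, but the g/dl figure comes first and is printed twice. Nothing settles the choice.
- *That adopting the g/l figure would make entry and appendix match.* Only the serum figures would match. Entry also admits patients by plasmacytoma, which is not among the three measurements in footnote d.
- *That the scoring doubt is confined to partial response.* The progression row also turns on measurable M-protein.
- *That every patient's eligibility is checked against source documents for each criterion.* The item "Source documents verifying every inclusion & exclusion criteria" belongs to the section 4 list for registering subsite patients: "Subsite patients will have eligibility verified and will be entered on study centrally". Patients at the sponsor's own site are registered by its coordinator under that office's standard practice, without such a list.

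**Conclusion.** Wrong as written. The two printed serum M-protein thresholds differ by a factor of 2.0 (5 versus 10 g/l, or 0.5 versus 1.0 g/dl). Patients with serum M-protein of 0.5 to <1.0 g/dl and no other qualifying measure are both eligible and ineligible on the text. Confidence in this is high; it rests only on unit conversion and on the measures being alternatives.

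The scoring ambiguity is held with moderate confidence. It requires that the g/dl figure governs and that footnote d is read as deciding when serum M-protein may be used at all.

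It would be tempting to conclude that the primary result or the error rates are compromised. The documents do not support that. They give no count of patients in the band, and the link from eligibility to the analysis is itself unsettled, since section 7.1.1 uses eligible treated patients and section 7.3 uses per protocol patients.

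**What to change.** The sponsor should reconcile the synopsis, section 3.1 and footnote d of section 13 to one serum M-protein threshold, stated with correct units. Which figure to keep is for the sponsor to decide.

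If the entry threshold stays below that in footnote d, footnote d should be aligned with it, so that every patient at or above the entry threshold is scored in the same way for response and progression. A sentence covering only patients admitted on serum M-protein alone would not be enough. A patient in the band who also qualifies by FLC faces the same choice between serum and FLC scoring.

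The cost is a correction to one line in each of two places, plus one line in the appendix if the lower figure is kept. The higher figure means a smaller eligible pool, by an amount the documents do not allow one to estimate. The lower figure means a stated departure from the response appendix as now printed.
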